- Change from baseline (mean of Screening and Day 1 values) in serum pre-albumin to the mean of Weeks 10 – 12 and albumin to Week 12
- Change from baseline (weekly mean of Screening) in ERI to Week 4 among patients
- Change from baseline (weekly mean of Screening) in ERI to the mean of Weeks 8 – 12

[figure not shown]
Exploratory

- Description of the systemic iron availability (TSAT, absolute reticulocyte count, hemoglobin, CHr) over time
- Description of markers of malnutrition-inflammation (pre-albumin and albumin) over time
- Description of systemic iron stores (serum ferritin, hepatic and splenic iron content by MRI, and supplemental iron dose requirements) over time
- Description of ERI change from baseline (weekly mean during the Screening Period) through Week 24
- Description of changes ESA and parenteral iron dose requirements from baseline (weekly mean during the Screening Period) to Evaluation Period (Weeks 8 – 12) and through Week 24
- Description of changes in LV mass index from Screening to Week 12

- Description of changes in pre-dialysis, post-dialysis, and delta-serum Troponin and NT-proBNP (defined as the difference between the pre- and post-dialysis troponin) from baseline (mean of Screening) to Weeks 10 – 11
- Description of handgrip strength from baseline (during Screening) to Week 12
- Description of the FACIT fatigue score from baseline (during Screening) to Week 12

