3.4 Duration of the Study

The total study duration for an individual patient will be approximately 9 months, excluding the Screening Period. The study periods are as follows:

- Initial Screening Period: Up to 2 weeks [Days -28 to -15]
 - Starts with the first date that Initial Screening procedures were performed. The first procedure also defines the Initial Screening visit date.
- Full Screening Period: up to 2 weeks [Days -14 through Day -1]
 - Starts with the date of the Week -2 Visit

- Treatment Period: 12 weeks [Week 1, Day 1 through Week 12]
 - Safety Follow-Up Period: 12 weeks [Weeks 13 through 24]
- Extended Follow-Up Period: 10 weeks [Weeks 25 through 35]

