5.3 Screening Visit Procedures (Days -14 to -1) – Full Screening

Prior to conducting any procedures, informed consent for the full study should be obtained and the Long ICF signed. The Long ICF includes consent for all study procedures subsequent to the Initial Screening.

Every effort should be made to obtain the blood tests for each visit on the same day of the week (e.g. on Wednesdays).

Important: Please note that ESA, IV iron, and dialysate iron dosing should be monitored carefully during this period as it is required to be stable (as defined in the inclusion criteria #8 and #9, [Section 4](#)) in order for patients to be eligible. Update standing orders for these medications as needed.

The following sections summarize the procedures for Week -2 and Week -1. Please see [Appendix A](#) for full details.

Week -2

- Dispense 3 fecal occult blood tests collection materials and review instructions for stool collection with the patient to avoid false positives (see Laboratory Manual for instructions). Request return of the samples within 1 week to allow sufficient time for analyses of these at the Central Laboratory. If necessary, stool occult blood testing may be performed locally if materials have not been returned in a timely manner.

Week -2 and Week -1

- On each of these weeks, obtain, before and after a single dialysis session: pre-dialysis and post-dialysis Central Laboratory tests, pre-dialysis and post-dialysis vital signs and weights, and record the net ultrafiltration (i.e. fluid removed minus fluid administered during dialysis) from the same dialysis session around which above procedures were performed.
 - At any time during these 2 weeks, perform a limited physical examination (see [Section 10.2.3](#)), obtain a 12-lead ECG (see [Section 10.2.2](#)), measure the handgrip strength, and have the patient complete the FACIT-F questionnaire.
 - Instructions for performing the handgrip strength and the FACIT-F questionnaire can be found in the Study Reference Manual
- Collect all 3 stool occult blood tests from patients and submit to the Central Laboratory. Locally performed stool testing may be substituted, if Central Laboratory results are not available prior to randomization.
- Record adverse events and any medication changes.
- Ascertain that the patient remains eligible before proceeding to the next visit
- Schedule the Day 1 visit to occur on a Monday, Tuesday, Thursday or Friday whenever possible.

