5.4.1 Week 1, Day 1 (First Dose)

- Randomize the patient
 - Randomization may be performed on Day -1, if needed. Administration of the first dose of Study Drug will continue to define Study Day 1.
- Prepare the Study Drug prior to the anticipated time of administration (see [Section 6.1.1](#) and Pharmacy Manual)
- Perform the hand grip strength prior to the start of dialysis (see instructions in the Study Reference Manual)
- Obtain Central Laboratory blood samples within 15 minutes prior to the start of dialysis
- Obtain a Local Laboratory (or point of care) INR (only for patients on warfarin)
- Obtain an ECG prior to the start of dialysis (see [Section 11.4.5.4](#))

- Have patient complete the FACIT-F questionnaire (see instructions in Study Reference Manual) prior to dialysis or during the first hour of dialysis
- Any time prior to the last one hour of dialysis, start the Study Drug infusion
- Obtain vital signs within 15 minutes prior to start of the Study Drug infusion, 15 ± 10 and 45 ± 10 minutes following the start of the Study Drug infusion and 0-15 minutes, 30-45 minutes, and 60-75 minutes following the end of the Study Drug infusion.
- Within 10 minutes after completing the Study Drug infusion, obtain blood samples
- Whenever feasible (e.g., first shift patients), obtain PK/PD blood samples 4 [+ 2] hours after completing the Study Drug infusion
- Record adverse events and any medication changes

5.4.2 *Week 1, Days 3 and 5*

- Obtain Central Laboratory blood samples within 15 minutes prior to the start of dialysis
- Obtain Central Laboratory blood samples within 10 minutes after the end of dialysis
- Record adverse event and any medication changes

5.4.3 *Week 2*

- Obtain Central Laboratory blood samples within 15 minutes prior to the start of dialysis
- Obtain a Local Laboratory (or point of care) INR (only for patients on warfarin)
- Obtain vital signs within 15 minutes prior to the start of dialysis
- Obtain Central Laboratory blood samples within 10 minutes after the end of dialysis
- Record adverse event and any medication changes

5.4.4 *Week 3*

- Prepare the Study Drug prior to the anticipated time of administration (see [Section 6.1.1](#) and Pharmacy Manual)
- Obtain Central Laboratory blood samples within 15 minutes prior to the start of dialysis
- Obtain a Local Laboratory (or point of care) INR (only for patients on warfarin)
- Any time prior to the last one hour of dialysis, start the Study Drug infusion

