[2] Serum pregnancy in women of childbearing potential only.

[3] Patients receiving warfarin only. May also be done using a point of care device.

[4] Obtain weight within 30 minutes prior to the start of dialysis. On Weeks 11 and 12, should be recorded for the same dialysis session during which Lab Panel 8 [CARD] data were collected.

[5] Limited physical exam to include skin, oropharynx, lungs, heart, abdomen, extremities (including feet), and any areas suggested by symptoms, with particular attention to signs of infection. May be performed by a physician-investigator or mid-level provider. Record abnormal findings in the source documents.

[6] Obtain blood pressure, heart rate, respiratory rate, and temperature: within 15 minutes prior to starting dialysis.

[7] On Day 1: Obtain blood pressure, heart rate, respiratory rate, and temperature: within 15 minutes prior to starting the infusion; 15±10 and 45±10 minutes following the start of the infusion and 0-15 minutes, 30-45 minutes, and 60-75 minutes following the end of the infusion.

After Day 1: Obtain blood pressure, heart rate, respiratory rate, and temperature: within 15 minutes prior to starting the infusion, 15 ± 10 and 45 ± 10 minutes following the start of the infusion; 0-15 minutes and 30-45 minutes following the end of the infusion.

[8] Within 30 minutes after the end of dialysis. Should be recorded for the **same** dialysis session during which Lab Panel 8 [CARD] was collected.

[9] Net ultrafiltration volume should be recorded for the **same** dialysis session during which Lab Panel 8 [CARD] data were collected.

[10] Obtain during Week 12 (+ 2 weeks).

[11] Perform handgrip strength any time prior to starting dialysis.

[12] Obtain blood pressure, heart rate, respiratory rate, and temperature: within 30 minutes prior to starting dialysis and within 30 minutes after dialysis.

[13] Have patient complete the FACIT-F questionnaire (see instructions in Study Reference Manual) prior to dialysis or during the first hour of dialysis. On Day 1, must be completed before the start of the Study Drug infusion.

[14] Visit window may be extended to +4 days only in instances when the study drug was missed on the targeted visit day and also could not be given during the dialysis visit after the missed dose.

[15] Randomization may be performed on Day -1, if needed. Administration of the first dose of Study Drug will continue to define Study Day 1.

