2.3 TIME WINDOWS FOR ANALYSIS

If data are collected by visit, the data will be analyzed by visit based on the protocol-planned visits. If multiple records are collected for a visit, the latest record will be used for the summary for that visit. Unless otherwise specified, baseline is defined as the last non-missing value prior to initiation of study drug. Early termination visit will be mapped to the post-baseline scheduled visit. After mapping, if there is more than one visit in the same window, the scheduled visit will be used if available. If there is no scheduled visit in the same window, the mapped visit closer to the target assessment day will be used. If more than one visit has the equal distance to the target day, then the later one will be used. The unscheduled visit will not be included in the by-visit summary, but will be included in the outlier analysis.

The observational period for the study will start from informed consent and end with study completion (see [Section 3.1](#) for the definition of study completion). Any event occurring after the defined observational period, even if collected on the CRF, may not be included in the summary statistical analysis. However, all data, including that reported after the defined observational period, will be included in the patient data listings.

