7.3 OTHER EFFICACY ANALYSES

Additional secondary objective is to explore the pharmacodynamic effects of COR-001 compared to placebo by evaluating changes in

- Change in hemoglobin from screening to peak hemoglobin (defined as per subject absolute maximal hemoglobin in g/dL)
- ERI and Hemoglobin from baseline (weekly mean during the Screening Period for ERI and mean of Full Screening and Day 1 for Hemoglobin) through Week 4, 12 and 24
- ERI and Hemoglobin from baseline (weekly mean during the Screening Period for ERI and mean of Full Screening and Day 1 for Hemoglobin) through Week 4, 12 and 24 stratified by baseline ERI tertiles
- ESA and parenteral iron dose requirements from baseline (weekly mean during the Full Screening Period) to Evaluation Period (Weeks 8 – 12) and through Week 24.

- Systemic iron stores (serum ferritin, hepatic and splenic iron content, and supplemental iron dose requirements) over time
 - Markers of malnutrition-inflammation (pre-albumin and albumin) over time
 - LV mass index from Screening to Week 12
 - Pre-dialysis, post-dialysis, and delta-serum Troponin and NT-proBNP (defined as the difference between the pre- and post-dialysis troponin) from baseline (mean of Screening) to Weeks 10 – 11.
 - Handgrip strength from baseline (during screening) to Week 12
- FACIT fatigue score from baseline (during screening) to Week 12

For the above efficacy variables, the observed values and changes from baseline will be summarized by treatment group using descriptive statistics for Pharmacodynamic analysis population.

Specifically, the weekly mean of ERI will be calculated and presented individually for each ESA based on the formula in [Section 1.2.3.2](#).

The mean of left and right handgrip strengths will be used for analysis no matter which hand is dominant.

The FACIT-F (Version 4) is a compilation of general questions divided into five primary domains: Physical Well-Being, Social/Family Well-Being, Emotional Well-Being, Functional Well-Being and Additional Concerns. The data in Additional Concern domain will be listed separately and considered the primary analysis for the FACIT-F. The total fatigue score will be calculated as a summation of the scores in the five primary domains. The observed value and change from baseline in total fatigue score will be summarized by treatment.

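### Handgrip and FACIT-F changes to Week 12 use a Screening-only baseline although both are measured again before the first dose; averaging the two pre-dose values would tighten the estimates at almost no cost

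*SAP*

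**What the plan says.** SAP 7.3 lists "Handgrip strength from baseline (during screening) to Week 12" and "FACIT fatigue score from baseline (during screening) to Week 12" among the other efficacy analyses. SAP 1.2.3.2 carries the same two items as exploratory endpoints. Protocol 3.1.3 does too, for example "Description of handgrip strength from baseline (during Screening) to Week 12".

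The measurement schedule is as follows.

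- **Full Screening (protocol 5.3 and Appendix A):** once, at any time in Week -2 or Week -1, sites are to "measure the handgrip strength, and have the patient complete the FACIT-F questionnaire". Protocol 3.4 closes this period on Day -1: "Full Screening Period: up to 2 weeks [Days -14 through Day -1".
- **Day 1, handgrip (protocol 5.4.1):** "Perform the hand grip strength prior to the start of dialysis". The drug is given during dialysis, so this value is pre-dose.
- **Day 1, FACIT-F (protocol Appendix A, Treatment Period footnote 13):** "On Day 1, must be completed before the start of the Study Drug infusion".

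Two other baseline rules sit beside this one. The general rule in SAP 2.3, where nothing else is specified, is that "baseline is defined as the last non-missing value prior to initiation of study drug". The laboratory endpoints in SAP 7.2 use the mean of the Screening (or Full Screening) and Day 1 values.

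SAP 7.3 summarises observed values and changes descriptively by treatment group in the pharmacodynamic population. It specifies no model and no test for these items.

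**The concern.** Day 1 lies outside Screening, so the second pre-dose value does not enter the baseline for the Week 12 change. The documents give no reason for this. Some other items in SAP 7.3, namely LV mass index and the cardiac markers, also use Screening alone, but they have no Day 1 measurement to add. Handgrip and FACIT-F do.

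Two things are at stake.

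- **Precision.** Physical function and fatigue are a stated secondary objective and feed the interim analysis in SAP 10.2. The comparison group is small: 2 placebo patients per cohort over 5 to 6 cohorts gives 10 to 12. A single baseline reading carries all of its occasion-to-occasion noise into the change.
- **Completeness.** SAP 2.4 does not impute missing values. Read literally, a patient with no Screening value has no change score even when Day 1 was measured.

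**Working it through.** **Inputs.** The documents state no SD, correlation, sample size or power for handgrip or FACIT-F. Protocol 11.1 and SAP 1.3.2 size only hsCRP, TSAT and CHr. There is therefore no figure of the plan's own to reproduce, and everything below rests on assumed correlations. From Appendix A, Week 12 is Day 78, which is 77 days after Day 1. Screening falls 1 to 14 days before Day 1.

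**Formulas.** Let S, D and W be the Screening, Day 1 and Week 12 values with common variance s². Let r = corr(S, D), a = corr(S, W) and b = corr(D, W).

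- Screening-only baseline: Var(W − S) = 2s²(1 − a)
- Averaged baseline: Var(W − (S + D)/2) = s²[1 + (1 + r)/2 − a − b]
- Saving from averaging: s²[(1 − r)/2 + (b − a)]

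The saving is positive whenever b ≥ a and r < 1, that is, whenever Day 1 tracks Week 12 at least as well as Screening does.

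**Equal correlations (r = a = b = ρ).** The variances are 2s²(1 − ρ) and 1.5s²(1 − ρ). Their ratio is 2/1.5 = 1.333 for any ρ. The Screening-only variance is 33% larger and the SD 15% larger (√1.333 = 1.155). A simulation of 1,000,000 draws at ρ = 0.7 also gave 1.333.

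**Baselines closer to each other than to Week 12 (a = b < r).**

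| r | a = b | Screening only (÷ s²) | Mean of two (÷ s²) | Ratio |
|---|---|---|---|---|
| 0.7 | 0.6 | 0.80 | 0.65 | 1.23 |
| 0.8 | 0.6 | 0.80 | 0.70 | 1.14 |
| 0.9 | 0.7 | 0.60 | 0.55 | 1.09 |
| 0.9 | 0.6 | 0.80 | 0.75 | 1.07 |

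**First-order decay with time.** Let the correlation at a lag of t days be w^(t/77). With w = 0.7:

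- Screening 1 day before Day 1: 0.6065/0.6009 = 1.01
- 7 days before: 0.6447/0.6064 = 1.06
- 14 days before: 0.6879/0.6126 = 1.12

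Over w from 0.5 to 0.9 the ratio runs from 1.01 to 1.13. In this pattern Day 1 alone does slightly better than the mean (0.600 against 0.6126 at a 14-day gap), but both do better than Screening alone.

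**Larger Week 12 variance, all correlations 0.7.** If the Week 12 variance is v·s², the two variances are s²[1 + v − 2a√v] and s²[(1 + r)/2 + v − (a + b)√v].

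- v = 1.25: 0.6848/0.5348 = 1.28
- v = 1.5: 0.7854/0.6354 = 1.24

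**Range.** Across these patterns the excess variance is about 1% to 33%. One third is not a mathematical ceiling. With r = 0.7, a = 0.6 and b = 0.7 the ratio is 0.80/0.55 = 1.45, but that needs Day 1 to track Week 12 markedly better than a Screening value at most two weeks earlier.

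**The case against.** The strongest reply is that a Screening baseline is a legitimate prespecified choice for descriptive, exploratory endpoints and that no decision rule depends on their precision. That stands, and it is why the point is minor.

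Four stronger readings are tempting, and the documents do not support them.

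- **That the variance is one third too large as a matter of fact, or that a third more patients would be needed.** This requires equal variances and equal correlations, which are nowhere stated. The two baselines are at most about two weeks apart and Week 12 is 11 to 13 weeks away, so some decay is plausible and would reduce the excess. Nothing here is powered, so a patient-equivalent has nothing to act on.
- **That the Day 1 value is thrown away.** SAP 7.3 also summarises observed values, and protocol 11.4.4 lists both measures over time. It names no Screening baseline there, so the protocol 11.3.3 default, the latest pre-dose evaluation, would apply. Day 1 is missing only from the baseline for the Week 12 change.
- **That SAP 7.3 contradicts SAP 2.3.** The default applies only where nothing else is specified, and naming Screening is such a specification.
- **That a practice effect between first and second test biases the result.** No section describes one. In a randomised comparison it would be expected in both arms, and averaging would still give the first test half the weight.

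The objection does not supply a reason to leave out a valid pre-dose value that patients and sites are already providing.

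**Conclusion.** The point holds as an improvement, not as an error. The Week 12 changes in handgrip and FACIT-F rest on one pre-dose reading where two are scheduled, unlike the laboratory endpoints in SAP 7.2. The unadjusted change-score variance is larger than it need be by up to about one third under equal variances and equal correlations, and by less, possibly only a few percent, if correlation decays with time. The direction of the gain requires only that Day 1 tracks Week 12 at least as well as Screening does, which is plausible because Day 1 is nearer. Recovering patients who lack a Screening value does not depend on any correlation. No primary, powered or tested endpoint is affected.

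**What to change.** In SAP 1.2.3.2, SAP 7.3 and protocol 3.1.3, define baseline for handgrip and FACIT-F along these lines:

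*Baseline is the mean of the Full Screening value and the Day 1 value obtained before the first dose; if one is missing, the other is used.*

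Apply it to each FACIT-F score that SAP 7.3 reports (the Additional Concerns domain and the total), and say whether the over-time summaries in protocol 11.4.4 use the same baseline. If Screening alone is intended, one sentence giving the reason would close the point.

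The cost is wording; no visit, procedure or data field changes. SAP section 12 allows for a SAP amendment. Changing the SAP alone would make it depart from protocol 3.1.3, so the protocol text should change too. That carries the usual amendment review and could be included in the next amendment. The change should be settled before treatment-level results on these measures are seen.

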Appendix E FACIT-F

FACIT-F (Version 4)

Below is a list of statements that other people with your illness have said are important. Please circle or mark one number per line to indicate your response as it applies to the past 7 days.

		Not at all	A little bit	Some- what	Quite a bit	Very much
PHYSICAL WELL-BEING						
GP1	I have a lack of energy	0	1	2	3	4
GP2	I have nausea	0	1	2	3	4
GP3	Because of my physical condition, I have trouble meeting the needs of my family	0	1	2	3	4
GP4	I have pain	0	1	2	3	4
GP5	I am bothered by side effects of treatment	0	1	2	3	4
GP6	I feel ill	0	1	2	3	4
GP7	I am forced to spend time in bed	0	1	2	3	4

		Not at all	A little bit	Some- what	Quite a bit	Very much
SOCIAL/FAMILY WELL-BEING						
GS1	I feel close to my friends	0	1	2	3	4
GS2	I get emotional support from my family	0	1	2	3	4
GS3	I get support from my friends	0	1	2	3	4
GS4	My family has accepted my illness	0	1	2	3	4
GS5	I am satisfied with family communication about my illness	0	1	2	3	4
GS6	I feel close to my partner (or the person who is my main support)	0	1	2	3	4
Q1	Regardless of your current level of sexual activity, please answer the following question. If you prefer not to answer it, please mark this box  and go to the next section.					
GS7	I am satisfied with my sex life	0	1	2	3	4

FACIT-F (Version 4)

Please circle or mark one number per line to indicate your response as it applies to the past 7 days.

EMOTIONAL WELL-BEING		Not at all	A little bit	Some-what	Quite a bit	Very much
GE1	I feel sad.....	0	1	2	3	4
GE2	I am satisfied with how I am coping with my illness.....	0	1	2	3	4
GE3	I am losing hope in the fight against my illness.....	0	1	2	3	4
GE4	I feel nervous.....	0	1	2	3	4
GE5	I worry about dying.....	0	1	2	3	4
GE6	I worry that my condition will get worse.....	0	1	2	3	4

FUNCTIONAL WELL-BEING		Not at all	A little bit	Some-what	Quite a bit	Very much
GF1	I am able to work (include work at home).....	0	1	2	3	4
GF2	My work (include work at home) is fulfilling.....	0	1	2	3	4
GF3	I am able to enjoy life.....	0	1	2	3	4
GF4	I have accepted my illness.....	0	1	2	3	4
GF5	I am sleeping well.....	0	1	2	3	4
GF6	I am enjoying the things I usually do for fun.....	0	1	2	3	4
GF7	I am content with the quality of my life right now.....	0	1	2	3	4

FACIT-F (Version 4)

Please circle or mark one number per line to indicate your response as it applies to the past 7 days.

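### SAP 7.3 calls Additional Concerns the primary FACIT-F analysis but defines and summarizes only a five-domain total, and states no item reversal or direction of benefit

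*SAP*

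**What the plan says.** SAP Section 7.3 describes FACIT-F (Version 4) as five domains and makes three statements about its analysis:

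- On the domain that matters most: "The data in Additional Concern domain will be listed separately and considered the primary analysis for the FACIT-F".
- On the score: "The total fatigue score will be calculated as a summation of the scores in the five primary domains".
- On what is reported: "The observed value and change from baseline in total fatigue score will be summarized by treatment".

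Earlier in the same section, a FACIT fatigue score is one of a list of variables for which "the observed values and changes from baseline will be summarized by treatment group using descriptive statistics for Pharmacodynamic analysis population". That sentence does not say which FACIT score is meant.

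The questionnaire is reproduced in Protocol Appendix E. Every item is answered from 0 (not at all) to 4 (very much), under the instruction "Please circle or mark one number per line to indicate your response as it applies to the past 7 days". Neither document states which items are reversed, what range a domain score has or which direction is better, and neither cites a scoring manual. The Study Reference Manual is cited only for completing the form.

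Protocol Section 2 places fatigue symptoms under a secondary objective. Protocol Section 3.1.3 and the SAP endpoint list treat the FACIT fatigue score as an exploratory, descriptive endpoint. SAP Section 10.2 includes it in the interim analysis.

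**The concern.** There are two separate problems.

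The first does not depend on how items are scored. The domain named as primary has no defined score and no stated treatment summary. The score that is defined and summarized carries the name fatigue, but most of it comes from items on physical, social, emotional and functional well-being. A reader of the study report would take the total as the fatigue result. A drug effect confined to fatigue would be diluted in it, and a change in, say, family support would move it.

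The second is that the direction of scoring is left open. Physical Well-Being includes "I have a lack of energy", where 4 is bad. Social/Family Well-Being includes "I feel close to my friends", where 4 is good. Emotional Well-Being is mixed: five items run one way, and "I am satisfied with how I am coping with my illness" runs the other. Additional Concerns is mixed too. The SAP writes out other derivations in full, such as the ERI formulas, the ESA unit conversion and the averaging of left and right handgrip. For FACIT-F, a programmer working from the SAP alone is told only to add.

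**Working it through.** The plan gives no FACIT-F figure to reproduce. No power or sample-size statement concerns this endpoint. The check therefore uses the 40 items in Protocol Appendix E.

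**Step 1: item direction.** Let N be the number of items worded so that 4 is worse, and P the number worded so that 4 is better. The two positive items in Additional Concerns are An5 and An7. The one in Emotional Well-Being is GE2.

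**Step 2: formulas.** If responses are summed as marked, the best possible state scores 4P and the worst scores 4N. A one-category improvement on every item changes the sum by P - N. If negative items are first reversed (4 minus response), the worst state is 0, the best is 4(N + P), and the same improvement gives N + P.

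**Step 3: results.**

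| Domain | N | P | Best, as marked | Worst, as marked | One-category improvement, as marked | One-category improvement, reversed |
|---|---|---|---|---|---|---|
| Physical | 7 | 0 | 0 | 28 | -7 | +7 |
| Social/Family | 0 | 7 | 28 | 0 | +7 | +7 |
| Emotional | 5 | 1 | 4 | 20 | -4 | +6 |
| Functional | 0 | 7 | 28 | 0 | +7 | +7 |
| Additional Concerns | 11 | 2 | 8 | 44 | -9 | +13 |
| Total | 23 | 17 | 68 | 92 | -6 | +40 |

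Summed as marked, the best and worst possible patients differ by 92 - 68 = 24 points on a 0 to 160 scale. The sign of a change also depends on where the improvement occurs:

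- Social plus Functional: 7 + 7 = +14 as marked, +14 reversed.
- Physical plus Additional Concerns: -7 - 9 = -16 as marked, 7 + 13 = +20 reversed.
- Additional Concerns plus Functional: -9 + 7 = -2 as marked, 13 + 7 = +20 reversed.

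**Step 4: dilution with correct reversal.** Additional Concerns supplies 13 of 40 items, or 32.5%. A one-category improvement confined to it is 13/52 = 25% of the range of the 13-item score but 13/160 = 8.1% of the range of the total. The other 27 items add variation that does not come from the domain named as primary.

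**The case against.** The strongest reply is that the SAP adds domain scores, not circled responses, and names a versioned instrument. A reader might infer from its silence that items are to be summed without reversal. The text does not say that. Appendix E is the form the patient completes, so the absence of a printed reversal there does not show how a domain is scored. This stands, and it makes the -6 versus +40 and -9 versus +13 comparisons conditional on summing responses as marked. They also assume an improvement on every item, which no document predicts. Within Additional Concerns, 11 of 13 items run the same way, so even a sum as marked keeps a readable sign (lower is better) with attenuation. Cancellation is severe only in the 40-item total.

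The second reply is that the general sentence in SAP 7.3 summarizes a FACIT fatigue score by treatment, and this could be Additional Concerns. A reader might infer from the FACIT-F paragraph that no summary of that domain is planned at all, and the general sentence leaves too much room for that to be certain. It does not settle the matter in the plan's favor either, because the only fatigue score the SAP defines is the five-domain total.

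The third reply concerns impact. The endpoint is exploratory and descriptive, has no test or power claim, and enters an interim analysis with no stopping rules. The item responses are collected and the Additional Concerns data are listed, so either score can be derived later. This also stands. A reader might infer that the fatigue objective cannot be answered. The documents do not support that, since the data needed will be available.

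**Conclusion.** The point holds as a defect of definition. Whatever the reversal practice, SAP 7.3 defines and summarizes a five-domain, 40-item total as the fatigue score and gives no defined treatment summary of the 13-item domain it calls primary. Followed as written, the plan reports a general well-being total as its fatigue result.

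Separately, no reversal rule or direction of benefit is stated for a form with 23 negatively and 17 positively worded items. If responses were summed as marked, the total could not be read as benefit.

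The consequence is limited to the fatigue result in the final and interim summaries. Safety and the hsCRP and SAA endpoints are untouched. At the interim, SAP 10.2 withholds subject numbers, minimum and maximum and shows only means, standard deviations and percentages, so a scoring error would be harder to notice there. The item classification rests on the wording in Appendix E alone, not on an outside scoring manual.

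**What to change.** Amend SAP 7.3 before the database is locked:

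1. Define the FACIT fatigue score as the 13-item Additional Concerns score, with the 11 negatively worded items reversed (4 minus response) and An5 and An7 kept as marked. State the range, 0 to 52, and that higher is better.
2. Make this score, with its change from baseline, summarized by treatment, the main FACIT-F result. Use the same definition for the interim analysis in SAP 10.2.
3. Report the five-domain total as supportive, scored in the same direction (0 to 160), under a name that does not contain the word fatigue.
4. State how a score is formed when an item is unanswered. The form lets patients decline GS7, and SAP 2.4 does not impute missing values by default. GS7 affects only the five-domain total, which is a further reason to lead with the 13-item score.

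The cost is a few lines of SAP text and a simple derivation. No new data are needed.
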